5 SAMPLE SIZE AND POWER

The number of subjects is not based on statistical power considerations.

6 STUDY PERIODS, TREATMENT GROUPS AND POPULATIONS FOR ANALYSES

6.1 Study Periods

The approximate duration of the study is 20 weeks (approximately 140 Days). This includes a 21 day screening period, a 12 week treatment period (6 weeks of response Phase and 6 weeks of remission phase) and a 1 month follow up period. The end of study will be defined as the date of the last visit of the last subject undergoing the study.

6.2 Treatment Groups

Treatment groups will be decided by the planned starting dose regardless of intra-subject dose escalation planned at day 57. Table 6.2-1 below indicates the planned treatment groups.

All summaries, except PK summary, will be provided by treatment group. For PK summary, it is current dose that is used to decide the dose group.

Table 6.2-1: Treatment Group

Cohort	Treatment Group Label
A	BMS 75mg
B	BMS 225mg
C	BMS 675mg
D	BMS 1500mg

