7.6 Safety

Analysis of safety will be based on All Treated Subjects and presented by treatment (“as treated”) and overall.

Adverse events (AEs) will be coded according to the most current version of MedDRA and be graded using the NCI Common Terminology Criteria for Adverse Events (CTCAE) version 4.0. Drug-related AEs are those events with relationship to study drug “Related” as recorded on the CRF. If the relationship to study drug is missing, the AE will be considered as drug-related.

Listing of adverse events will include all enrolled subjects as SAEs and deaths are collected pretreatment. Summaries of adverse events will include (1) events occurring from the first dose date to 35 days (inclusive) after the last dose of BMS-986004 for subjects who are off study

treatment and (2) all events occurring from first dose date for subjects who are still on study medication.

When reporting adverse events by CTC grade, summary tables will be provided based on the event with worst CTC grade (independent of relationship to study medication). Subjects will only be counted (1) once at the preferred term (PT) level, (2) once at the system organ class (SOC) level, and (3) once in the 'Total subject' row at their worst CTC grade, regardless of SOC or PT.

The analysis of laboratory results will be based on All Treated Subjects. Laboratory results will be categorized according to NCI CTCAE (version 4.0) grade. Baseline is defined as the last non-missing measurement prior to the first dosing date and time. Summaries of laboratory results include baseline and (1) post-baseline results up to 35 days (inclusive) after the last dose of BMS-986004 for subjects who are off study treatment and (2) all available post-baseline results for subjects who are still on study medication.

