7.6.1 Overall Adverse Events

AEs will be tabulated by descending frequency of SOC and descending frequency of PT within each SOC, unless specified otherwise.

Summary:

Overall summary of any AEs by worst CTC grade (grade 1, 2, 3, 4, 5, unknown) presented by SOC/PT for each treatment group and arm.

Listing:

All recorded Adverse Events occurring in the pre-treatment, on-treatment, and post treatment period will be listed.

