7.6.2 Deaths

Summary:

All deaths during the study within 35 days after the last dose of BMS-986004 will be summarized for cause of deaths by treatment group and arm.

Listing:

All recorded deaths during the study, including post-treatment follow-up period, and deaths that resulted from a process that began during the study, will be listed.

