7.6.3 Serious Adverse Events

Summary:

Overall summary of SAEs by worst CTC grade (grade 1, 2, 3, 4, 5, unknown) presented by SOC/PT for each treatment group and arm.

Listing:

By-subject SAE listing will be provided for the All Enrolled Subjects.

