7.6.5 Multiple Events

Analyses that take into account the multiple occurrences of a given adverse event will be conducted. In order to prepare these analyses, the CRF data will be processed according to standard BMS algorithms in order to collapse adverse event records into unique records based on the preferred term. This data will be presented as the rate per 100 patient-years of exposure. This analysis will take into account all on-treatment events (allowing more than 1 event per subject) and the total duration of exposure. The patient-years exposure will be computed as the sum over the subjects’ exposure expressed in years where the duration of exposure is defined as

- Date of last dose of study treatment - date of first dose of study treatment +35 + 1 days, for subject who are off study treatment and were followed at least 35 days after last dose of study medication.
- Last known date alive - date of first dose of study medication +1, for subjects who are still on-treatment or who are off study treatment and were followed less than 35 days after last dose of study medication.

Summary:

The following summary tables will be provided for each arm:

Total number and rate (exposure adjusted) of occurrences for all AEs occurring in at least 5% of the subjects treated in the arm.

For select AEs, if applicable:

Tables showing the number of subjects experiencing an AE once or multiple times in each arm

Listing:

Unique instances of all AEs, i.e., after duplicates have been eliminated and overlapping and contiguous occurrences of the same event (i.e. same PT) have been collapsed.

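### SAP 6.2 puts safety findings that arise after Day 57 escalation under the lower starting dose, and no visible safety summary uses the dose received at onset

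*SAP*

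**What the plan says.** SAP 6.2 sets the grouping rule: "Treatment groups will be decided by the planned starting dose regardless of intra-subject dose escalation planned at day 57". Its scope is stated next: "All summaries, except PK summary, will be provided by treatment group". PK is the one exception and is grouped by current dose; SAP 7.7.1 spells out which escalated subjects join which dose group on Day 71.

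SAP 7.6 opens the safety section with "Analysis of safety will be based on All Treated Subjects and presented by treatment". It then adds *as treated* in parentheses and an overall presentation. Summaries run from first dose to 35 days after last dose, which covers all escalated dosing. On counting it says "Subjects will only be counted (1) once at the preferred term (PT) level", and likewise once per system organ class and once in total, at worst grade.

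The individual tables use these columns:
- Adverse events (7.6.1): "presented by SOC/PT for each treatment group and arm". The SAE table (7.6.3), "Overall summary of SAEs by worst CTC grade", has the same columns.
- Deaths (7.6.2): "will be summarized for cause of deaths by treatment group and arm".
- Multiple events per 100 patient-years (7.6.5): "The following summary tables will be provided for each arm", with no mention of treatment group.
- Laboratory grades (7.6.7): one worst on-treatment grade per subject and test, by treatment group and arm. Descriptive laboratory statistics are by treatment and study day.

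Neither *as treated* nor *arm* is defined. SAP 7.4 plans no analysis of extent of exposure; the number of subjects escalated appears only with the efficacy summaries (7.4, 7.5.4). SAP 8 leaves table detail to a Data Presentation Plan.

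**The concern.** The primary objective is the safety and tolerability of multiple doses. A subject who starts in cohort A, B or C and escalates at Day 57 takes four infusions at one dose and up to three at the next. Under 6.2 that subject has one dose column, the lower one. Because the adverse event and laboratory-grade tables keep one worst grade per subject, an escalated subject's entry can come from either dose and the table cannot show which.

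A reader who wants tolerability at 225, 675 or 1500 mg will look in those columns, which leave out the experience of subjects escalated into that dose. The 75, 225 and 675 mg columns include experience gained at a higher dose. The documents use dose received elsewhere: PK is regrouped by current dose, and Protocol Appendix 1 assumes that the adverse event rate depends on the highest dose a subject takes.

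No between-dose safety test is planned, so what is at stake is the descriptive reading of safety by dose, not an error rate.

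**Working it through.** The plan gives no figure for this point. Its one sample-size figure, the 90% interval for 4 of 10 responders, reproduces as the exact interval (0.150, 0.696), but it has no bearing here. The size of the issue has to be derived.

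**Inputs.** Ten subjects per cohort (SAP 2.1). Planning response rates 0.2, 0.4 and 0.55 at 75, 225 and 675 mg (Protocol Appendix 2); expected range 20–50% (SAP 7.7.3). First escalated dose Day 57, last dose Day 85 (SAP 2.1). Summary window to last dose + 35 days (SAP 7.6). Laboratory visits from Protocol Table 5.1-2. Assumptions: all subjects complete, all non-responders escalate, none enters the long-term extension (LTE).

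**1. Subjects with two doses in one column.** Escalated = 10 × (1 − response rate).
- 75 mg: 10 × 0.8 = 8; 225 mg: 10 × 0.6 = 6; 675 mg: 10 × 0.45 = 4.5. Sum 18.5 of 30.
- SAP range: 30 × 0.5 = 15 to 30 × 0.8 = 24.
- If three quarters of non-responders escalate: 0.75 × 18.5 = 13.9.

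**2. Visits that feed the worst laboratory grade.** Post-baseline visits to Day 120 (85 + 35): Days 2, 4, 8, 15, 29, 43 and 50 (7 before); Day 57; Days 71, 72, 75, 78, 85, 99 and 113 (7 after). Total 15 per subject, 150 per column. Share after Day 57 in escalated subjects = escalated × 7/150:
- 75 mg: 56/150 = 37%; 225 mg: 42/150 = 28%; 675 mg: 31.5/150 = 21%.
- At three-quarters escalation: 28%, 21% and 16%.

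These are opportunities for a worst grade, not shares of worst grades.

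**3. Person-time in 7.6.5, only if *arm* there means a dose cohort.** Completer's window = 85 − 1 + 35 + 1 = 120 days; from Day 57 on = 85 − 57 + 35 + 1 = 64 days. Column share = (escalated/10) × (days from Day 57/window).

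| Window | 75 mg | 225 mg | 675 mg |
|---|---|---|---|
| To Day 120 (64/120) | 43% | 32% | 24% |
| To Day 113, 4-week follow-up in the SAP (57/113) | 40% | 30% | 23% |
| To Day 85, window in Protocol 5.3 (29/85) | 27% | 20% | 15% |

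At three-quarters escalation the first row is 32%, 24% and 18%. These are shares of time, not of events.

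**4. What *arm* changes in 7.6.5.** The table is limited to events in at least 5% of the arm. In a cohort of 10, one subject (10%) passes. If *arm* means all 40 subjects, 5% is 2 subjects, and no rate by dose is given at all.

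**The case against.** Starting-dose grouping is a sound main display. It agrees with Protocol 5.3, which asks for summaries by dose cohort and for all doses combined, and it keeps the groups unselected by response. Columns by dose at onset would be confounded: after Day 57 mainly responders remain at the starting dose in cohorts A to C, and time on drug and carry-over differ. With about ten subjects per cohort, dose at onset can be traced by hand from the adverse event and dosing listings and from the 7.5.4 report of Day 1 and Day 57 doses. Laboratory descriptive statistics are by study day, so values before and after Day 57 sit in separate rows, although escalated and non-escalated subjects stay mixed after it. Cohort escalation does not rest on these tables: the early decision rule counts titrated subjects separately, and the DMC reviews safety before each new cohort. All of this stands. It limits the point to a missing supplementary display and unclear terms.

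A reader might infer more, which the documents do not support:
- *That these events appear only under the lower dose.* They also enter the overall column and the listings.
- *That 6.2 and 7.6 contradict each other.* *As treated* may mean the starting dose actually received, and *arm* may mean the overall column. The terms are undefined and not reconciled with 6.2, which is less than a proven contradiction.
- *That 43%, 32% and 24% of events are mislabelled.* Those are person-time shares, and they apply only if 7.6.5 has dose-cohort columns.
- *That no dose-at-onset table is planned.* None is visible in the SAP, but the Data Presentation Plan was not available.

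**Conclusion.** The point holds as a gap in the descriptive safety reporting and should be fixed before the tables are produced. The 6.2 rule is explicit, and 7.6 does not say how a subject who took two doses is classified. About 18.5 of 30 subjects in cohorts A to C would carry two doses in one column, 15 to 24 on the SAP's own range.

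The counts are approximate. Escalation uses a criterion of 50,000/mm³ with a rise of at least 20,000/mm³, which the planning rates are not stated to use and which may mean more escalation. It also requires a favorable safety profile, which may mean less. Without LTE entry, cohort D and non-escalated subjects are unaffected. The SAP reflects the protocol only through Amendment 02 and does not cover the LTE. In the current protocol a cohort 3 subject who enters it receives 1500 mg from short-term Day 85, so the affected group widens if those events enter the same tables. No rate ratio or direction of bias is inferred.

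**What to change.** Keep the starting-dose tables as the main display and make these changes to the SAP:

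1. Define *as treated* and *arm*, and cross-refer 7.6 to 6.2.
2. Add descriptive adverse event, SAE and laboratory-grade summaries by dose received at onset or assessment, derived from actual dosing dates: starting dose until the first escalated infusion, current dose from then on. Pre-infusion Day 57 samples belong to the starting dose.
3. Show last dose received in the death table.
4. Print the number escalated in the safety table headers.
5. If 7.6.5 is presented by dose, split patient-years at the first escalated infusion.
   - Before = date of first escalated dose − date of first dose.
   - After, if followed at least 35 days past the last dose = date of last dose − date of first escalated dose + 35 + 1. Otherwise = last known date alive − date of first escalated dose + 1.
   - Check: 56 + 64 = 120 days for a completer; 56 + 57 = 113 if last known alive at Day 113.
6. State how events and person-time after LTE entry are handled or excluded.

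The cost is SAP wording, one derived variable from dosing records already collected, and a few extra tables. The SAP should state the downside: a subject can appear in two dose columns, and the post-Day 57 columns are confounded with response status, time on drug and carry-over, so they support description only.

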6.3 Populations for Analyses

- All Enrolled Subjects, defined as all subjects who signed an informed consent;
- All Treated Subjects, defined as all subjects who have received at least one dose of study treatment;
- Pharmacodynamic Population, defined as all subjects that receive any study medication and have PD biomarker data available,
- Pharmacokinetic Population, defined as all subjects who receive any study medication and have any available concentration-time data. Additionally, the evaluable PK Population is defined as subjects who have adequate PK profiles.

All available derived PK parameter values will be included in the PK data set and reported, but only subjects with adequate PK profiles will be included in the summary statistics and statistical analysis.

7 STATISTICAL ANALYSES

SAS® version 9.2 or higher will be used for statistical analyses, tabulations and graphical presentations. S-Plus® version 8.1.1 or higher may also be used for graphical presentations. Exploratory analysis may be done with R or other software tools.

7.1 General Methods

All data recorded on case report forms will be listed by subject. Descriptive summaries will be presented for continuous variables using number of subjects (N), mean, standard deviation (SD), median, minimum and maximum. Geometric mean and coefficient of variation (%CV) will also be presented for sample serum concentration-time data and PK parameters. Descriptive summaries for categorical variables will utilize counts and percentages.

Adverse events and medical history will be coded according to the most recent Medical Dictionary for Regulatory Activities (MedDRA). Previous and concomitant medications will be coded using the WHO Drug Dictionary.

7.2 Study Conduct

Relevant deviations from the study protocol, protocol amendments and administrative changes will be documented and accounted for in presenting the data summaries, listings and descriptive statistical analyses. Deviations of protocol-specified inclusion and exclusion criteria will be listed. Any changes from planned protocol-specified analysis will be defined in the SAP and reported in the CSR.

7.3 Study Population

7.3.1 Subject Disposition

Subject disposition will be listed. Summary tables reflecting the number of subjects who are enrolled, who are treated, reasons for not entering treatment period and who completed the study will be presented for each treatment group and all.

7.3.2 Demographic Characteristics

Demographic characteristics such as gender, age, race and ethnicity will be listed for all treated subjects. Demographic characteristics will also be summarized for all treated subjects for each treatment group and all.

7.3.3 Physical Measurements

Physical measurements such as body weight, height and body mass index (BMI) will be listed for all treated subjects. Measurements will also be summarized at baseline by treatment group and overall for all treated subjects.

7.3.4 Medical History, Previous and Current Medications

Medical history will be listed for all treated subjects. Previous and current medication will be listed in ascending order of date for all treated subjects. In addition, rescue medications, if any, will be listed.

7.3.5 Study Procedure

Any conducted medical treatment procedures and utilized diagnostic procedures will be listed.

7.4 Extent of Exposure

Study drug administration and container number will be documented as per subject listings. No analysis regarding extent of exposure is planned. However, number of subjects having dose-escalation per treatment group will be provided along with efficacy summarizes (please see details in [Section 7.5.4](#))

7.5 Efficacy

Efficacy results are assessed by platelet counts and bleeding SMOG scores obtained longitudinally through the study. The collection date and time are available in [Table 7.10-1](#) (Both are collected at the same day).

7.5.1 Derivation of Efficacy Endpoints

Primary efficacy criteria and response category:

- Response (R) - platelet count $\geq 30,000/\text{mm}^3$ and at least 2-fold increase from the baseline count and absence of bleeding.
- Complete Response (CR) - platelet count $\geq 100,000/\text{mm}^3$ and absence of bleeding.
- No Response (NR) - platelet count $< 30,000/\text{mm}^3$ or less than 2-fold increase of baseline platelet count or bleeding.
- Not Assessable (NA) - platelet count is missing or is excluded due to rescue medication.

Subject's best response is decided in the order of CR, R, NR, and NA.

Secondary efficacy criteria and response category:

- Clinically Significant Response - platelet count $\geq 50,000/\text{mm}^3$ with an increase of at least $20,000/\text{mm}^3$ from baseline and absence of bleeding.
- No Clinically Significant Response - platelet count $< 50,000/\text{mm}^3$, or increase of $\leq 20,000/\text{mm}^3$ from baseline, or bleeding.
- Not Assessable (NA) - platelet count is missing or is excluded due to rescue medication.

Absence of bleeding:

Absence of bleeding is defined as SMOG scores being zero for all the three major domains (Skin, visible mucosae, and organs) with ITP-BAT on the same day when platelet count is assessed.

Platelet data exclusion and rescue medication flag:

Platelet counts collected within 4 weeks after any rescue medication, though still shown in listing of figures of raw data, will be excluded from summarizing platelet and deriving subject response. To facilitate the exclusion, rescue medication flag may be derived and included in some analysis datasets and listings if at least one subject takes rescue medication after the first dosing during the trial. Rescue medication flag is set to Y (Yes) within 4 weeks after the day any rescue medication is administered, i.e., between rescue medication day and rescue medication day + 27, inclusively. It will be set to N (No) when otherwise.

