7.5.3 Platelet Count

Bleeding SMOG score, platelet count, platelet change from baseline, potentially rescue medication flag, and response category (each under primary and secondary efficacy criteria) at each study day will be listed for all treated subjects.

Platelet count and change from line will be summarized by treatment group for each study day. Percent of visits with platelet count $\geq 30,000/\text{mm}^3$, $50,000/\text{mm}^3$, and $100,000/\text{mm}^3$ will be listed for each subject and summarized for each treatment group.

Platelet count and its change from baseline may be explored by graphs and statistical models. Details are available in the section of exploratory biomarker analysis.

Exploratory analysis of platelet count is shown in section 0.

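### SAP 7.5.1 makes counts from the rescue day to day +27 Not Assessable and never scores rescue as failure, so same-day pre-rescue counts are lost and duration and percent-of-visits can look better than under failure scoring

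*SAP*

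**What the plan says.** **The exclusion.** SAP 7.5.1 addresses "Platelet counts collected within 4 weeks after any rescue medication". These stay in the listings and raw-data figures but "will be excluded from summarizing platelet and deriving subject response". The flag that implements this is set "between rescue medication day and rescue medication day + 27, inclusively".

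**The category.** Both the primary and the secondary response criteria in SAP 7.5.1 have a class for such visits: "Not Assessable (NA) - platelet count is missing or is excluded due to rescue medication". At subject level, "Subject's best response is decided in the order of CR, R, NR, and NA".

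**The summaries affected.** In SAP 7.5.3, platelet count and change from baseline "will be summarized by treatment group for each study day". The percent of visits at or above 30,000, 50,000 and 100,000/mm³ "will be listed for each subject and summarized for each treatment group". The section does not say whether Not Assessable visits stay in the denominator.

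**Duration of response.** SAP 4.1 ends it at disease progression, which the visible SAP does not define, and otherwise censors at the last platelet measurement. Protocol 5.4.2 ends it at loss of CR or R. Neither names rescue.

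**Rescue itself.** Protocol 1.5.5 allows it for severe bleeding, wet purpura or an investigator's judgement of immediate risk, and says its purpose is to raise counts. SAP 7.3.4 plans only a listing of rescue use. Much of Protocol 3.4 is redacted, so this point rests on the visible text.

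**The concern.** Keeping rescue-lifted counts from passing as drug response is right. The difficulty is that the affected visits become missing rather than failed. The permitted reasons for rescue are signs that the subject is doing badly, so the missing visits are informative about outcome.

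Two features of the SAP 7.5.1 wording add to this.

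- **Start of the window.** The sentence in words covers counts taken after rescue, but the flag starts on the rescue day itself. A sample drawn that day before rescue cannot have been raised by it, yet it is dropped.
- **Overlapping classes.** Bleeding alone is enough for No Response. A rescue-day visit with bleeding therefore fits both No Response and Not Assessable, and no visit-level precedence is given; the stated ordering is for best response only. SAP 7.5.2 treats each bleeding assessment as covering the interval since the previous one, so the rescue-day score is evidence about the period before rescue.

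At stake are the secondary and exploratory descriptive summaries: duration of response, percent of visits above threshold and per-visit means, in cohorts of 10 where one rescued subject can move a group figure.

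**Working it through.** **Inputs.** Window: rescue day to day +27 (SAP 7.5.1). Post-dose platelet visits (Protocol Table 5.1-2): Days 2, 4, 8, 15, 29, 43, 50, 57, 71, 72, 75, 78, 85, 99, 113, 127 and 141, which is 17. The documents give no rescue frequency and no platelet levels around rescue, so the subject data below are assumptions.

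**1. Window length.** 27 − 0 + 1 = 28 days, which reproduces the stated 4 weeks, but only by counting the rescue day. Applied to the schedule, one rescue on a visit day removes 1 visit (Day 141) to 5 visits (Day 2, 50, 57, 71 or 72).

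**2. Percent of visits.** Assume two visits at or above 30,000/mm³, both outside the rescue windows.

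| Rescue day(s) | Visits removed | Not Assessable visits leave denominator | Kept as not above threshold |
|---|---|---|---|
| 29 and 71 | 29, 43, 50; 71, 72, 75, 78, 85 (8) | 2/9 = 22.2% | 2/17 = 11.8% |
| 29 only | 29, 43, 50 (3) | 2/14 = 14.3% | 2/17 = 11.8% |

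A rescue on Day 57 removes Days 57, 71, 72, 75 and 78. A subject above threshold on Days 15, 29, 43 and 50 only scores 4/12 = 33.3% against 4/17 = 23.5%. If also above on Days 85 to 141, the scores are 9/12 = 75.0% against 9/17 = 52.9%. A subject never above threshold scores 0% either way.

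The SAP describes a one-month follow-up, ending at Day 113 in its PK table. With those 15 visits the first table becomes 2/7 = 28.6% and 2/12 = 16.7%, each against 2/15 = 13.3%. The direction is unchanged.

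**3. Per-visit mean.** With 1 of 10 subjects rescued, the other nine averaging M and the rescued subject's off-rescue count L (thousands/mm³), exclusion reports M, and keeping the low value gives (9M + L)/10. The difference is (M − L)/10.

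- M = 40, L = 20: 40 against 38, difference 2.0.
- M = 100, L = 5: 100 against 90.5, difference 9.5.

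**4. Duration.** Assume response from Day 29 and a low pre-rescue count on Day 57, the rescue day, and read the SAP end event as loss of response.

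- Day 57 counted as loss: (57 − 29)/7 = 4 weeks.
- SAP rule, Day 85 low: (85 − 29)/7 = 8 weeks.
- SAP rule, response from Day 85 on: censored at (141 − 29)/7 = 16 weeks, or (113 − 29)/7 = 12 weeks with the shorter follow-up.
- Low count drawn the day before rescue: it is retained and the loss is dated correctly, to within a day of 4 weeks.

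**5. Comparator check.** Against as-observed data the direction reverses when rescue lifts counts. If Days 71 to 78 are lifted above threshold after a Day 57 rescue, the 33.3% compares with 8/17 = 47.1%, the 75.0% with 13/17 = 76.5%, and the 0% with 4/17 = 23.5%. If the rescued count is 150, means of 40 and 100 compare with (360 + 150)/10 = 51 and (900 + 150)/10 = 105.

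**6. Best response.** In the order CR, R, NR, NA, removing visits can delete a qualifying response but cannot create one. Recoding Not Assessable to No Response moves only a subject with no assessable visit at all.

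**The case against.** The strongest reply is that the affected items are descriptive. The primary endpoint is safety, there is no formal hypothesis, and the sample size is not power-based. Setting confounded counts aside is a recognised strategy, and it stops rescue-lifted counts from passing as response. Flagged counts still appear in listings and raw-data figures, and bleeding is listed and summarised in its own right. All of this stands. It limits the weight of the point but does not supply the missing rules.

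A reader might infer more than the documents support:

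- **That the response rate is inflated.** It is not; step 6 shows why.
- **That percent-of-visits is biased upward as written.** If Not Assessable visits stay in the denominator, the SAP already gives 2/17. The demonstrable fault is that the denominator is unstated. The two-rescue example is also a large case, because visits cluster after Day 71.
- **That the count prompting rescue is always lost.** It is lost only if drawn on the rescue day. The visible text gives no platelet trigger, and bleeding may be the prompt.
- **That the rule raises results outright.** This holds only against failure scoring.
- **That dose response is flattened.** This would need rescue to be commoner at less effective doses, which the documents do not state. Subjects never above threshold show no percent-of-visits effect at all.

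**Conclusion.** The point holds in a limited form. As written, SAP 7.5.1 discards same-day pre-rescue counts against its own description of the window, and no visible rule lets a rescue register as non-response or loss of response.

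Compared with failure scoring, and on the assumed data:

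- duration of response can go from 4 weeks to 8, or to 16 censored, depending on how the undefined end event is read and on counts after day +27;
- per-visit means are about 2 to 9.5 thousand/mm³ higher for one rescued subject in ten;
- percent-of-visits rises by about 2.5 points (one Day 29 rescue) to 10.4 points (rescues on Days 29 and 71), and by 9.8 or 22.1 points in the two Day 57 examples, provided that excluded visits leave the denominator and the subject was above threshold elsewhere.

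Best-response rate is not inflated. The trial-level size cannot be given because rescue frequency is not stated. The SAP should settle these rules before the data are summarised.

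**What to change.** 1. **Window start.** Begin the exclusion after the rescue administration time, so that same-day pre-rescue counts and bleeding scores are kept. State what applies when a time is missing.
2. **Visit-level scoring.** Score rescue-window visits as No Response, and keep them in the percent-of-visits denominator as not meeting the threshold. State that denominator in SAP 7.5.3.
3. **Duration.** Treat rescue as loss of response in this analysis, and reconcile the SAP end event (disease progression) with the protocol's (loss of CR or R).
4. **Per-visit means.** Keep the present exclusion for counts after rescue, and report at each visit how many subjects were excluded for rescue.

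The cost is SAP wording and programming, plus confirmation that sampling and rescue times are recorded. Percent-of-visits and duration figures become slightly less favourable. The recoding neither adds nor removes responders in the best-response counts.
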